10. HUMAN SUBJECTS

Inclusion criteria are HIV-seropositive, age ≥ 50 years, diagnosis of chronic non-cancer pain, English speaking and consents to study participation.

Exclusion criteria are cancer-associated pain, unwillingness to participate in audio recorded sessions, and enrollment in hospice.

Upon signing informed consent, the participant is considered enrolled in the study.

The exclusion criteria noted above was developed to prevent the confounding nature of cancer associated pain. We will be excluding monolingual Spanish speaking individuals as this will likely impact group dynamics of therapy. Monolingual Spanish speaking individuals aging with HIV in chronic pain is a group we will consider evaluating in future studies if our intervention demonstrates efficacy.

We will recruit persons who receive medical care at the Owen Clinic with chronic non-cancer pain (i.e. pain > 3 months that is not cancer-related) who are ≥ 50 years old. Common co-morbidities include mental illness (24% with anxiety disorders, 12% with mood disorders, 3% with schizophrenia and 5% with other psychiatric disorders), substance use disorders including tobacco and alcohol (75% have a current or past history) and poverty (43% of the population is on Medicaid, 26% is on Medicare and 8.9% is on a healthcare plan for low income PLWH or Ryan White) which enhances the real-world translatability of this intervention. Of note 8% of all Owen clinic attendees prefer Spanish, but it is

unknown what proportion are monolingual Spanish only. Demographics of PLWH ≥ 50 years on > 3 months of opiate prescriptions (and thus underestimate the chronic pain population) are presented (Table 1).

Psychosocial co-morbidities and coping strategies in PLWH differ between men and women, and sex may be a modifying variable(85-87). To address sex as a biological variable, I will recruit at least 20% women and if needed rely on the Center For AIDS Research Disparities Core to achieve this ([name] Letter of Support).

Table 1. aPLWH on > 3 months of opiates for chronic pain at Owen Clinic (January 5, 2017)

	N = 355
Age years mean (range)	56 (50-70)
Sex	
Male	255 (71.8%)
Female	100 (28.2%)
Race/Ethnicity	
White	235 (66.1%)
Black	76 (18.5%)
Asian	2 (0.6%)
Native American	2 (0.6%)
Other	40 (11.3%)
Hispanic	52 (15%)
HIV Outcomes mean (range)	
CD4 T cells/mL ²	608 (1439)
HIV Viral load <20	363 (80.3%)

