For AIM 3 Acceptability and Feasibility of Adapted ACT Intervention: Forty persons will be randomized to either group adapted ACT or group education. In anticipation of ~15% early discontinuation or lost to follow up, we plan to recruit 50 participants overall. All sessions will be audio recorded for future analysis. Adapted ACT will be provided by ACT therapists in weekly 2-hour group (8-10 persons per group) sessions for the 6 weeks of the intervention and will include brief review of at-home practice assignments, introduction of new material and end with assigned at-home practice exercises. Participants randomized to control will also participate in 2-hour 6 weeks group sessions (8-10 persons) using the “Take Charge of Your Pain” handbook developed by Investigators at the Weill-Cornell Translational Research Institute for Pain in Later Life (Table 2). All sessions will be audio recorded for future analysis. Study participants will complete assessments at baseline, week 3 (midpoint) and week 6 (endpoint). Following completion of study we will assess for persistence of ACT activities and practices by a short telephone follow up. Participants may come to the AVRC for an in person discussion but this will not receive monetary compensation.

Remote Engagement of Study Participants

To ensure safety of participants (who are all older adults with the co-morbidity of HIV) during COVID-19 and respect the “shelter at home” state-wide order this aim will be performed 100% virtually. The protocol specifically has been adapted to include

- 1) over the phone consent. This is a minimal risk study and with COVID-19 the risk of an in-person evaluation greatly outweighs the potential benefit.
- 2) Questionnaires to be completed via a) online through REDCAP mechanism that provides a link and password to allow participants to securely complete questionnaires or b) complete paper questionnaire mailed to participant with stamped envelope for return with only the study ID on papers to protect participant privacy
- 3) Online group meetings using Zoom with password to prevent hackers.
- 4) Compensation provided either using an electronic gift card or a script mailed to the study participant.

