Telephone or in Person Feedback from Each Session

Within 48 hours of the session each participant will be contacted by [name] or another trained member of the study team and will inquire about the experience of each individual. This will include aspects of the class they liked most and least. These surveys will also employ open-ended questions about program content.

Long-Term Follow Up

Each participant will be contacted via telephone 3, and 6 months after completion of the group ACT sessions by [name] or another trained member of the study team and will inquire about persistence of ACT practices and strategies participants recommend for ongoing use of ACT. Specifically we will ask if they are continuing ACT practices.

Step 2 Adapted ACT RCT

Screening Assessment (Week 0)

Screening will be identical to Step 1.

Entry Evaluations and Randomization

Subjects will be randomized (1:1) to ACT versus education control. A total of 20 subjects (10 per arm) will be randomized and followed for the duration of the six weeks of the intervention and control. Once ten participants are enrolled into one group that will start that adapted ACT intervention will start. At study entry baseline surveys will be collected using paper CRF or web-based computer assisted system (to view baseline survey see Appendix III) similar to Step 1.

On-Study Evaluations

Study specific follow-up visits for each subject will be kept to a minimum in order not to bias the outcome of lost to follow up. Participants will undergo pain and acceptability questionnaires at week 3 (Appendix VI). These will be repeated along with psychosocial co-morbidity questionnaires at week 8. Participants

will be provided \$20 for completion of baseline assessments, \$30 for midpoint and \$50 for endpoint assessments.

Instructions for Evaluations

Documentation of HIV

Documentation of HIV-1 infection will be confirmed by reviewing a positive test from any licensed screening antibody test, such as ELISA, and confirmed by a second antibody test, such as Western blot, or detectable plasma HIV-1 RNA at any time prior to study entry. If an ELISA or Western Blot is not available, HIV infection may be documented by two HIV RNA values \geq 2000 copies/mL, drawn at least 24 hours apart. The RNA assays should have been run at CLIA approved laboratory or equivalent.

Medical and Laboratory History

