study design, and incorporate an intent-to-treat (ITT) approach to analyze the outcome data. We will employ multivariable logistic regression analysis to study the association between clinical (duration of HIV infection, nadir CD4, BPI), demographic (i.e., age, sex, duration of HIV infection, nadir CD4), and psychosocial factors (i.e., substance use, loneliness) and intervention arm adjusting for baseline demographic and clinical characteristics. Variables significantly associated with treatment groups and outcome ($p < 0.10$) including appropriate interaction terms, will be included in the final multivariable logistic regression model as covariates. CSQ at midpoint and proportion of sessions attended will be evaluated in sensitivity analyses. The study procedures can occur in person or remotely. We will statistically evaluate this process and compare group cohesion scores between persons who attend live (if feasible) and remotely.

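### Sex is called a possible modifier, but the stated 1:1 allocation is not stratified by sex, and the p<0.10 covariate screen would miss a 6:2 split of women

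*Combined protocol and SAP*

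**What the plan says.** Section 10 (Human Subjects) states that co-morbidities and coping differ between men and women and that "sex may be a modifying variable". The response given there is "To address sex as a biological variable, I will recruit at least 20% women", with outside recruitment help if it is needed. The denominator of the 20% is not stated. Table 1 of that section shows 100 women among 355 clinic patients (28.2%).

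On allocation, Section 9 (Step 2, Entry Evaluations and Randomization) says "Subjects will be randomized (1:1) to ACT versus education control". The supplied text names no stratification, blocking or minimisation.

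On size, Section 9 (Aim 3) says "Forty persons will be randomized to either group adapted ACT or group education" and "In anticipation of ~15% early discontinuation or lost to follow up, we plan to recruit 50 participants overall". The Step 2 text says "A total of 20 subjects (10 per arm) will be randomized".

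On analysis, the Analytic Plan in Section 9 compares baseline characteristics between arms, using Fisher's exact test for categorical variables. It lists sex among the candidate factors: "demographic (i.e., age, sex, duration of HIV infection, nadir CD4". Variables associated with treatment group and outcome at p<0.10, "including appropriate interaction terms, will be included in the final multivariable logistic regression model as covariates". No sex-by-arm term is named. The section defers to an SAP that takes precedence, but no further SAP text is supplied.

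**The concern.** A floor on recruitment secures that some women are enrolled. It does not control how they fall between arms, and it does not say what will be reported about them. With few women and unrestricted 1:1 allocation, a lopsided split is not rare.

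The analysis rule is a weak safeguard. It decides whether to adjust for sex by testing sex against arm, and with so few women that test has little chance of flagging a noticeable imbalance. The same rule also lets interaction terms in on the strength of the data, in a sample too small to support them.

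At stake is a tidier primary comparison on the CSQ, and an honest statement of what a pilot of this size can say about sex.

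**Working it through.** **Inputs.** 40 randomised, or 20 by the Step 2 text; 1:1 allocation; floor of 20% women; 28.2% women in the clinic table. Three further inputs are my assumptions, because the documents give no SD, alpha or effect size: fixed equal arms, a CSQ analysed as continuous in SD units, and two-sided 5%.

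**The plan's own figures.** 100/355 = 28.2%, as stated. For recruitment, 40/(1 − 0.15) = 47.1, or 48 in equal arms. The stated 50 is close to that, and 50 × 0.85 = 42.5 would complete.

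**Number of women.** 0.20 × 40 = 8; 0.282 × 40 = 11.3, taken as 11; 0.20 × 20 = 4. If the floor applies to the 50 recruited, it is 10.

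**Split between arms.** The number of women k in one arm is hypergeometric: P(k) = C(w,k) C(N−w, N/2−k) / C(N, N/2).

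- N=40, w=8: P(0)=0.0016, P(1)=0.0202, P(2)=0.0958. Both tails: 2 × 0.1176 = 23.5% for 6:2 or worse. For 7:1 or worse it is 4.4%, and all in one arm is 0.3%. With independent coin-toss allocation, 6:2 or worse is 28.9%.
- N=40, w=11: 2 × (0.0621 + 0.0138 + 0.0016 + 0.0001) = 15.5% for 8:3 or worse.
- N=50, w=10: 28.9% for 7:3 or worse.
- N=20, w=4: 2 × (0.2477 + 0.0433) = 58.2% for 3:1 or worse. No women in one arm: 2 × 0.0433 = 8.7%.

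**Would the p<0.10 screen see it?** The plan does not name the screening test, so I use Fisher's exact test, which it names for categorical baseline variables. For 20 per arm and 8 women, 6:2 gives p=0.235 and is not flagged; 7:1 gives p=0.044. As written, the variable must also be associated with outcome.

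**Size of the confounding.** A 6:2 split is 6/20 = 30% against 2/20 = 10% women. The unadjusted arm difference shifts by 0.20 × (sex effect on CSQ). For a sex effect of 0.5 SD (assumed), that is 0.10 SD. The standard error of the arm difference is √(2/20) = 0.32 SD.

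**Precision of a sex-by-arm effect.** SE = √(1/Wa + 1/Wb + 1/Ma + 1/Mb), with women (W) and men (M) in arms a and b; 95% half-width = t(N−4) × SE.

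| N | Women by arm | SE (SD) | 95% half-width (SD) |
|---|---|---|---|
| 40 | 4:4 | √0.625 = 0.79 | 2.028 × 0.79 = 1.60 |
| 40 | 6:2 | 0.89 | 1.81 |
| 40 | 5:6 | 0.71 | 1.44 |
| 40 | 10:10 | 0.63 | 1.28 |
| 20 | 2:2 | 1.12 | 2.37 |

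For a true interaction of 1.0 SD, power is 23% at 4:4 and 34% even with equal numbers of men and women.

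**The case against.** The strongest reply is that this is a pilot with acceptability as its primary outcome, and that it never promises to estimate modification by sex. Sex is not ignored: it is a candidate covariate, and baseline characteristics are compared between arms. Twenty per cent is a minimum with support to reach it, and the clinic's 28.2% points to about 11 women. At the floor, 76% of allocations are 3:5, 4:4 or 5:3. Chance imbalance in one covariate is part of the sampling error of any randomised comparison. Much of this stands, and it keeps the point small.

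It also rules out some stronger readings that a reader might infer:

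- *Sex is treated as an established or likely modifier.* The text says only that it may be one.
- *The missing stratification makes modification impossible to estimate.* With 8 of 40, women fall in both arms in more than 99% of allocations. The 1.60 SD half-width already assumes a perfect 4:4 split. The limit is the sample size.
- *A poor split would seriously bias the CSQ comparison.* The shift is 0.2 times the sex effect at 6:2.
- *Women must be spread across therapy groups.* No passage sets a rule on group composition by sex or says that it affects the outcome. This is an optional preference.

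What the reply does not answer is the screen. It would miss 6:2, and it leaves the door open to data-selected interactions.

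**Conclusion.** The point holds as a minor design and analysis improvement. At the recruitment floor with 40 randomised, there is about a one in four chance of a 6:2 or worse split of women, and the stated p<0.10 rule would not adjust for 6:2. With 11 women, the chance of 8:3 or worse is 15.5%. If 20 is the true total, imbalance is the usual result (58% at 3:1 or worse), and one arm has no women with probability 8.7%. The conflict between 40 and 20 therefore has to be settled before any of these figures is final.

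The harm to the primary comparison is modest, at 0.10 SD for an assumed 0.5 SD sex effect. Any sex-by-arm estimate would be uninformative under every split considered.

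The conclusion rests on fixed equal arms, a continuous CSQ and the supplied text alone. The SAP to which the protocol defers could name a stratification factor. The logistic model in the plan would be less informative still, with separation possible in cells this small.

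**What to change.** 1. Reconcile the two randomised totals in Section 9.
2. Stratify the 1:1 allocation by sex, which is known at screening, using concealed lists with varying block sizes because the trial is un-blinded. If this is not done, state why.
3. Include sex as a prespecified factor in the CSQ comparison, not one selected at p<0.10.
4. State that CSQ and attendance will be described by sex within arm with 95% confidence intervals, and that no sex-by-arm interaction will be selected or tested.

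The cost is slightly more randomisation set-up and a few sentences, with no extra participants. The downsides are some predictability of allocation in the small female stratum, which varying blocks reduce but do not remove, and a more modest claim about sex. Stratification protects the split; it does not make the sex-by-arm estimate useful.

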11. RECRUITMENT AND PROCEDURES PREPARATORY TO RESEARCH

Study Recruitment and Retention: Previously successful recruitment strategies will be employed including using CNICS infrastructure to identify eligible participants at Owen Clinic for provider-based referrals, self-referral through flyers placed in each exam room, and presentations to relevant community organizations. For pre-screening recruitment purposes ONLY, we are requesting for a partial waiver of informed consent to interrogate the EPIC database and identify potential prospective research participants who meet the eligibility criteria for enrollment as listed in Item 10 Human Subjects.

The investigator believes the pre-screening to be used for recruitment meets the following requirements for this request per 46 CFR 46.116:

1. The (pre-screening) procedure is considered no more than minimal risk to the potential subjects, since we will not perform any procedure and the probability and magnitude of harm or discomfort anticipated in the research are not greater than those ordinarily encountered in daily life.
2. The waiver or alternation will not adversely affect the rights and welfare of the subjects.
3. The (pre-screening) research could not practicably be carried out without the waiver or alternation; and.
4. Once the potential participants are identified, we will contact their PCP and ask them to distribute one of our IRB-approved flyers. If interested, study participants will contact the study team and schedule a screening visit (per IRB-approved study protocol). Whenever appropriate, the subjects will be provided with additional pertinent information after participation.

Recruitment procedures will also involve the review of subject records by designated study personnel (e.g., investigators and/or study coordinators) in order to identify potentially eligible subjects. Since Protected Health Information (PHI) will be accessed via the hospital's medical record database prior to contacting the potential subject about the research study, we are requesting a partial waiver of HIPAA authorization for access to PHI for purposes of prescreening only.

For HIV-infected participants recruited through the Owen Clinic, we request a partial waiver of consent to screen the Owen Clinic database for eligible participants. A list of potential eligible participants will be printed and will include the name and contact information of the responsible primary care physician. Study personnel will contact primary care providers via phone or in person and ask them to distribute study flyers. Potential participants will be contacted only through their primary care providers. Study personnel will not contact any potential participant directly. The list of name will be destroyed as soon as the providers are informed. If interested, potential study participants can contact the AVRC and schedule a screening visit.

If additional participants are needed to fulfill our recruitment needs we will seek IRB approval before distributing any recruitment materials and will implement our standard AVRC recruitment plan as described below.

Standard HIPAA authorization to collect research data from the subject's medical record will be obtained at the time of informed consent.

A brief subset of preliminary eligibility criteria such as age, gender, and sexually transmitted disease diagnosis in the past 12 months, will be reviewed by study personnel to determine subjects' preliminary eligibility for the research study. There will be no direct contact of the potential research subject by the pre-screener (i.e., study staff). The pre-screener will ask the subject's treating physician to approach the subject. The treating physician will further discuss the research study with the potential subject and ask whether they would like to be contacted by study staff to discuss the trial (i.e., counseling) and/or provide the potential subject with the study staff's contact information. Eligibility may be formally

determined at the time of counseling, but any research-specific screening procedures will only be performed after informed consent is obtained and a standard, stand-alone HIPAA authorization form is signed.

For the partial waiver of individual authorization for pre-screening recruitment purposes ONLY of individual HIPPA/Protected Health Information. The following conditions apply:

1. The (pre-screening) research involves no more than minimal risk, since we will not perform any procedure and the probability and magnitude of harm or discomfort anticipated in the research are not greater than those ordinarily encountered in daily life.
2. Granting of waiver for recruitment purposes only will not adversely affect privacy rights and welfare of the individuals whose records will be used.
3. The pre-screening could not practicably be conducted without a waiver.
4. The pre-screening could not practicably be conducted without use of PHI.
5. The privacy risks are reasonable relative to the anticipated benefits of research.
6. An adequate plan to protect identifiers from improper use and disclosure is included in Item 16.
7. Participant identifiers/sensitive information shall be removed/destroyed as soon as they are no longer needed and in accordance with AVRC policy. The investigators have procedures in place to periodically review collected participant identifiers/sensitive information to ensure it is still required to satisfy a particular purpose or carry out a function.
8. The participants' PHI will not be re-used or disclosed for other purposes.

The standard AVRC step-by-step recruitment plan is delineated by the following four steps: 1) Educate potential participants and promote study enrollment using flyers and media in waiting rooms and in treatment rooms at UCSD clinics and other likely recruitment sites throughout the community, e.g., local hospital psychiatry services, community based organizations, local pharmacies, etc.; 2) Station recruitment staff in clinics (e.g., UCSD's Owen Clinic) to work with providers in identifying individuals potentially eligible for the research study; where appropriate and with IRB consent, these activities may include reviews of clinical charts; 3) Conduct outreach and informative presentations to staff and potential participants at identified recruitment sites; 4) List the study on AVRC website for potential participants. This website is known throughout the San Diego HIV community to be a resource for HIV-related information; 4) Ask identified study participants to recruit others who may be eligible for inclusion using established sampling techniques (e.g., snowball sampling, respondent driven sampling).

However, now that a majority of outpatient visits are being performed using video visits – potential participants are no longer being exposed to study flyers in clinic. We request Owen clinic providers be allowed to recommend this study using mychart communications. We also propose to utilize social media – such as facebook, Instagram and twitter to recruit potential participants. Only approved wording (as indicated in the study flyer) will be included.

Philosophy of recruitment

Working with a population experiencing the complex issues of HIV disease, we have found that it is especially important to have flexibility in the assessment schedule. Thus, the assessment schedule designed for this project has the necessary flexibility to adapt to the real-life complexities of working with this clinical population. For example, visits can be scheduled Monday – Saturday and can be completed in one visit or split over multiple visits. Procedures are also in place to overcome barriers such as lack of transportation, need for childcare or dependent care, and other factors. Reminder calls

are also provided. Participants who miss a visit are contacted and the reasons that contributed to the missed visit are examined. Planned future visits take this information into account and make accommodations whenever possible.

